3 PROTOCOL SUMMARY

Protocol Number:	3324582_B	
Protocol Title:	ASSURE WCD Clinical Evaluation - Detection and Safety Study (ACE- DETECT)	
Study Objectives	Primary: To evaluate ambulatory detection performance of the ASSURE Wearable Cardioverter Defibrillator (WCD)	
	Secondary: To evaluate arrhythmia detection performance and safety of the ASSURE WCD	
Study Population:	Adult cardiac patients at risk for sudden cardiac arrest	
Study Design:	Multicenter single arm open label evaluation	
Number of Subjects:	At least 130 subjects (maximum 135) with at least 35 of each sex, male and female	
Study Sites:	Subjects will be enrolled at approximately 10 clinical sites in the United States, with each site enrolling a maximum of 18 subjects.	
Eligibility Criteria:	Candidates are eligible for participation if they meet all Inclusion Criteria and none of the Exclusion Criteria.	
	Inclusion Criteria:	
	1. Males or females, age ≥ 18 years	
	2. Patients with an active Implantable Cardioverter Defibrillator (ICD)	
	 Left Ventricular Ejection Fraction (LVEF) ≤ 40%, measured within the past year (12 months) by echocardiography, nuclear imaging (including MRI), or left ventricular angiography 	
	 Able and willing to provide written informed consent before undergoing any study-related procedures 	

	Exclusion Criteria:
	 Any condition that by the judgement of the physician investigator precludes the subject's ability to comply with the study requirements, including cognitive and/or physical limitations that would prevent the subject from interacting with the device as intended
	2. Any known skin allergy or sensitivity to the study garment materials that will be next to the skin
	3. Any breached or compromised skin on the upper body that would be exacerbated by wearing the study garment
	 Work with or are frequently around equipment that produces high electromagnetic fields, for example magnetic resonance imaging devices, power supply facilities, or welding equipment
	 Any planned surgical or medical procedures during the participation period that would require the subject to remove the study device for more than 12 hours
	6. Any planned air travel during the participation period
	7. Pregnancy
	8. Use of mechanical circulatory support, including but not limited to Left Ventricular Assist Device (LVAD) or Total Artificial Heart
	9. Implanted Cardiac Resynchronization Therapy Defibrillator (CRT-D)
	 Simultaneous plan/prescription for Holter monitor, mobile cardiac outpatient telemetry (MCOT), Event Recorder, or in-hospital telemetry
	 Use of any electronic medical device that is worn on or near the body requires Sponsor approval, other than continuous positive airway pressure (CPAP), continuous blood glucose monitor, or pulse oximeter oxygen saturation (SpO₂) monitor.
	12. Under bust chest circumference greater than 52 inches or less than 28
	inches
	13. Current hospital inpatient
Device:	ASSURE [™] WCD with shock alarms and shock functionality disabled. Shock Alarm Event Markers are recorded by the WCD and will be used for analysis of the primary outcome measure.
Study Procedures:	At Visit 1 subjects will be fitted with the WCD and will be trained and provided written instructions for use, including safety precautions and adverse event reporting. Demographic data and limited medical history will be collected and subjects will be asked to complete a baseline comfort scale. Subjects will wear the device for approximately 30 days during normal daily activities including sleep. Research Coordinators will conduct weekly phone interviews with the subjects during the participation period to address subject questions, review potential adverse events, and review usage. Subjects will return for a final visit, Visit 2, at the end of the wear period. At Visit 2 subjects will be interviewed

	regarding any adverse events they may have experienced since the most recent phone follow up, and status of any adverse events that were recorded during the participation period. They will be asked to complete a Device Usability Survey. The device will be removed and returned. They will be asked to complete a follow up comfort survey. All episodes recorded by the ASSURE WCD and/or the subject's ICD will be reviewed by independent clinical experts.
Study Endpoints:	
Primary:	WCD False Positive Alarm Rate (False Positive Alarms per subject-day)
Secondary:	Summary of WCD True Positive Detections and Missed Events (False Negative Detections)
	Estimated Inappropriate Shock Rate
	Adverse Events
Study Duration:	Individual subject participation is approximately 30 days. Total study duration from first subject in to last subject out is approximately 4 Months.

5 GLOSSARY OF ABBREVIATIONS AND DEFINITION OF TERMS

ABBREVIATION	TERM
AADE	Anticipated Adverse Device Effect
AE	Adverse Event
BMI	Body Mass Index
CFR	Code of Federal Regulations
CIED	Cardiovascular Implantable Electronic Device
CPAP	Continuous Positive Airway Pressure (Sleep Apnea Therapy)
CRF	Case Report Form
CRT-D	Cardiac Resynchronization Therapy Defibrillator
ECG	Electrocardiogram
FDA	Food and Drug Administration
GDR	General Document Record
ICD	Implantable Cardioverter-Defibrillator
ICF	Informed Consent Form
IDE	Investigational Device Exemption
IRB	Institutional Review Board
ITT	Intent-to-Treat
LVAD	Left Ventricular Assist Device
LVEF	Left Ventricular Ejection Fraction
МСОТ	Mobile Cardiac Outpatient Telemetry
MI	Myocardial Infarction
NSR	Non-Significant Risk (Medical Device)
PP	Per Protocol
RC	Research Coordinator
SAE	Serious Adverse Event
SAF	Safety (set of subjects for statistical analysis)
SAP	Statistical Analysis Plan
SCA	Sudden Cardiac Arrest
SID	Subject Identification Number
SpO2	Pulse Oximeter Oxygen Saturation
SVT	Supraventricular Tachycardia
UADE	Unanticipated Adverse Device Effect
VF	Ventricular Fibrillation
VT	Ventricular Tachycardia
WCD	Wearable Cardioverter Defibrillator

6 INTRODUCTION

Background

The Wearable Cardioverter-Defibrillator (WCD) is indicated for adult patients who are at risk or at perceived risk of sudden cardiac arrest (SCA) and are not immediate candidates for or refuse an implantable defibrillator.

These patients are defined by two populations. The first population includes those patients for whom there may be optimism for clinical improvement, for example, patients soon after revascularization or those with a recent diagnosis of myocardial infarction (MI) or cardiomyopathy in whom guideline directed medical therapy is being initiated. The optimal management of these patients during the waiting period before ICD implantation is currently unknown. The second population includes those patients who have a clear indication for an ICD but also have a contraindication to immediate ICD placement, for example, active infection or unknown prognosis. (Piccini JP)

The study Sponsor has developed a new wearable defibrillator, the ASSURE WCD, to address this need. This study is part of a comprehensive set of tests which has been proposed to establish safety and effectiveness of the ASSURE WCD and will be included in support of the Premarket Approval (PMA) application for the ASSURE WCD.

Previous Clinical Studies

Second Generation Prototypes:

- Protocol 3322262: Single-center non-randomized study to evaluate Electrocardiogram (ECG) signal quality, comfort and usability; 5-day wear period; 6 healthy normal adult subjects (Sponsor employees, 4 males, 2 females) enrolled; 2 non-serious minor severity adverse events (AEs) observed (skin irritation) after five days of wear. ECG signal analysis and comfort/usability data used to improve various aspects of garment and electrode design in the next generation prototype.
- Protocol 3325053: Multi-center (Seattle and Florida) non-randomized study to evaluate ECG signal quality, comfort and usability enrolling adult subjects from the community with age and body-habitus representative of device intended use; 5-day wear period; 12 healthy normal adult subjects (8 females, 4 males) enrolled; 5 non-serious minor AEs and 1 non-serious moderate severity AE observed (all skin irritation) after five days of wear. The moderate severity AE was minor severity skin irritation due to the garment wear that was then

exacerbated by the subject scratching the area. ECG signal analysis and comfort/usability data were used to improve various aspects of garment and electrode design in the next generation prototype.

- Protocol 3321770: Single-center (University of Washington Medical Center) non-randomized study to evaluate ECG signal quality, comfort and usability enrolling adult cardiac subjects with low ejection fraction (≤ 40%), age and body-habitus representative of device intended use; 2-day wear period; 50 subjects enrolled (30 males, 20 females, average age 58, age range 34-90); 1 nonserious minor severity AE observed (skin irritation) after two days of wear. ECG signal analysis and comfort/usability data were used to improve various aspects of garment and electrode design in the next generation prototype. ECG and accelerometer signals were used to support Rhythm Analysis Algorithm (RAA) development.
- Protocol 3324914: Usability, non-randomized, study to evaluate comfort of WF2 prototypes and subject responses to simulated WF2 prototype system notification (alert) messages (low critical battery, adjust garment, and therapy) for 48 hours in subjects' home environments. A total of 10 subjects were enrolled from the general population (5 females, 5 males, average age 64.8, age range 56-74) each received 20 alert messages during the 48-hour study duration. No AEs were reported during the 48-hour study duration and subjects responded to simulated system notification messages during the day and night.

Third Generation Prototypes:

- Protocol 3330766: Multi (6)-center non-randomized study to collect ECG and accelerometer signals to support RAA development and assess comfort and usability; enrolling adult cardiac patients with low ejection fraction, age and body-habitus representative of device intended use; 5-day wear period; 117 subjects enrolled (40 females, 76 males, average age 60.1 age range 30-82). Nine (9) AEs were reported that were all related to skin irritation; 8 minor severity and 1 originally minor severity that was exacerbated to moderate severity after the subject scratched the area of irritation.
- Protocol 3333597: Single center (Swedish Sleep Medicine Sleep Lab) randomized study to assess subject response time to high priority alerts (shock alarms) during one night's sleep. Subjects were randomized at enrollment to one of 12 simulated alarm scenarios. 12 subjects from the general population were enrolled (5 males/ 7 females) with average age of 69 (range 43-73). 24 shock alarms were issued (2 to each subject). Mean response time to shock alarm

during sleep was $(7.0 \pm 2.5 \text{ seconds})$. There was one shock alarm that was "missed" (subject failed to respond in 20 seconds or less). No AEs were reported.

Protocol 3334121: Single center randomized study to assess subject response time to high priority alerts (shock alarms) during normal daily activities. Subjects were randomized to one of three simulated alarm scenarios implemented over a 7-day wear period. 20 subjects from the general population were enrolled (9 males/11 females) with average age of 57 (range 41-71). 55 shock alarms were issued. Mean response time to shock alarm during normal daily activities was 13.3 ± 10.1 seconds. There were eleven shock alarms that were "missed" (subject failed to respond in 20 seconds or less). One minor AE reported (skin irritation).

Fourth Generation Prototypes:

Protocol 3335586: Multicenter (3) non-randomized study to evaluate safety and detection performance of the ASSURE wearable cardioverter defibrillator (WCD) device during a typical 30-day prescription period; 32 subjects enrolled in the US from the general population (16 females, 16 males, average age 61.7, age range 40-73). This was a pilot study for the pivotal clinical study (ACE-DETECT). 8 AEs were reported in 6 subjects (2 subjects experienced 2 AEs each). 7 AEs were related to skin irritation and 1 was scratches from the garment seam; All 8 were minor severity.

Study Rationale

A WCD provides continuous arrhythmia monitoring with detection of potentially fatal ventricular arrhythmias and automatic defibrillation. The ASSURE WCD incorporates an automatic Rhythm Analysis Algorithm (RAA) that uses patient ECG to determine if a patient should be treated with a defibrillation shock. The device also provides vibratory, audible, and visual alerts to the patient when a shockable rhythm is detected and before a shock is delivered. If the patient is conscious during this "shock alarm", they will be able to defer a shock using a divert button on the WCD.

Because shockable rhythms occur infrequently in the target population, RAA sensitivity to shockable rhythms and specificity to non-shockable rhythms has been validated in the final ASSURE device using a robust, statistically-valid dataset of previously acquired rhythms.

Kestra Medical Technologies, Inc. Protocol 3324582_B

False shock alarms are another important WCD performance metric. Medical device alarms in general have been recognized as a top health technology risk. Excessive alarms, particularly those for conditions that aren't clinically significant or for conditions that could be avoided, such as alarms that result from poor contact between an ECG electrode and the patient's skin, can lead to alarm fatigue and ultimately patient harm (ECRI Institute). In the case of the WCD, excessive alarms also contribute to lack of compliance (Duncker T). The LifeVest® 4000 Operator's manual (ZOLL Medical Corporation) indicates that false alarms occur at a rate of 2.0 per patient week of use (one every 3.4 days). Similarly, high alarm rates are reported in several other published and un-published studies of the LifeVest (Dillon K); (Schuhmann CG); (Duncker T); (Hucker W). Signal interference (ECG noise) is reported as the primary cause of false alarms.

7 INVESTIGATIONAL DEVICE

Description

The WCD used for this study will be controlled by the Sponsor from managed inventory designated for clinical evaluations only. The devices will be production-equivalent systems with shock alarms disabled (Shock Alarm Event Markers will be recorded by the device for analysis purposes), defibrillation therapy programmed OFF, and detection parameters at default settings. Detection parameter default settings include Ventricular Tachycardia (VT) rate threshold at 170 bpm and Ventricular Fibrillation (VF) rate threshold at 200 bpm.¹

[figure not shown]
The ASSURE™ Cardiac Recovery System is comprised of several components:

- A WCD including a Garment with embedded ECG sensors that is worn on the body next to the skin, a Monitor which houses the battery and the graphic user interface, Cable Assembly which connects the Garment to the Monitor, and a Carry Pack
- A Charger that allows recharging of the monitor batteries
- A Tablet that allows the WCD to be programmed via wireless connection to the Monitor
- CareStationTM website which allows users to view WCD data associated with study subjects
- An ASSISTANT[™] mobile device that allows data uploads from the WCD to CareStation website

The ASSURE Cardiac Recovery System is illustrated in Figure 1.

¹ Accuracy of the ASSURE WCD heart rate measurement for tachyarrhythmias is +/- 10%

Figure 1 ASSURE Cardiac Recovery System

Device Regulatory Classification

The Sponsor has assessed this as a minimal risk study using a Non-Significant Risk Device. The study will be governed by the abbreviated Investigational Device Exemption (IDE) Requirements [21 CFR 812.2(b)]. The rationale for this assessment is based on the configuration with shock alarms disabled and shock functionality programmed OFF.

Safety and Accountability

Risks have been identified through systematic hazard analysis. The Sponsor has documented risk mitigation in a controlled Risk Management Report. Each component of the WCD is assigned a unique serial number that is included on the labeling. Labeling also includes "CAUTION: Investigational Device. Limited by Federal (USA) law to investigational use", and the Sponsor's name and address in accordance with 21 CFR 812.5. The Sponsor will maintain tracking records for all system components.

Sizes and Fitting

Multiple sizes of the garment will be available for this study. In addition, there are two garment styles: one more suitable for male subjects, and one with support more suitable for female subjects. Subjects will be measured to select an appropriate size, then the garment fit will be adjusted while on the subject to ensure it is adequate for reliable data collection. Each subject will be assigned two garments so when they wash one, they can continue wearing the system using the other garment.

Reuse of System Components

The Garment, which is the component of the system that will come in direct contact with the study subject and includes the dry-contact electrodes, and the Carry Pack, will *not* be re-used for other study subjects. All other components of the system will be cleaned and disinfected by the Sponsor and will undergo safety testing before reuse.

Devices will be stored at ambient room temperature in a secure location. Access should be strictly limited to the Investigators and their designees. Neither the Investigators nor any designees may provide devices to any individual not participating in this protocol.

Device Accountability

Sites will maintain accurate records of inventory and dates of receipt of all devices.

For regulatory requirements regarding device accountability, all device accountability will be reconciled during study monitoring. Study devices must be returned to the Sponsor according to applicable state and federal regulations.

Kestra Medical Technologies, Inc. Protocol 3324582_B

All Study System components returned by the site must be accompanied by a copy of the Product Accountability Log for the respective kit dispensed. No devices or device components should be destroyed.

8 INVESTIGATIONAL PLAN

This is a multicenter single arm open label study enrolling adult patients at risk for sudden cardiac arrest.

Number of Subjects

At least 130 subjects (maximum 135) will be enrolled with at least 35 of each sex, male and female.

Study Sites

Approximately 10 sites in the United States are planned to participate in this study, with each site enrolling a maximum of 18 subjects.

Participation Period

Subjects will wear the device for approximately 30 days. This period was selected to correspond to the WCD prescription period² while providing sufficient data to test the performance hypothesis.

Study Objectives and Endpoints

Primary Objective: To evaluate ambulatory detection performance of the ASSURE WCD.

Primary Endpoint: WCD False Positive Alarm Rate (FPA) calculated as False Alarms per subject-day.

Secondary Objectives: To evaluate arrhythmia detection performance and safety of the ASSURE WCD.

Secondary Endpoints: Summary of WCD True Positive Detections and Missed Events (False Negative Detections), estimated inappropriate shock rate, and summary of adverse events determined to be at least possibly related to the device.

² Medicare classifies the WCD as capped rental Durable Medical Equipment (DME) with a monthly payment. A Written Order Prior to Delivery (WOPD) is required to initiate the prescription, and continued use requires documentation justifying continued medical need such as by a prescription refill or completion of Certificate of Medical Necessity (CMN). The WCD is described by Healthcare Common Procedures Code Set (HCPCS) K0606, Automatic external defibrillator, with integrated electrocardiogram analysis, garment type.

Target Population

Adult cardiac patients at risk for sudden cardiac arrest

Eligibility Criteria

Candidates are eligible for participation if they meet all Inclusion Criteria and none of the Exclusion Criteria.

Inclusion Criteria

- 1. Males or females, age ≥ 18 years
- 2. Patients with an active Implantable Cardioverter Defibrillator (ICD)
- Left Ventricular Ejection Fraction (LVEF) ≤ 40%, measured within the past year (12 months) by echocardiography, nuclear imaging (including MRI), or left ventricular angiography
- 4. Able and willing to provide written informed consent before undergoing any study-related procedures

Exclusion Criteria

- 1. Any condition that by the judgement of the physician investigator precludes the subject's ability to comply with the study requirements, including cognitive and/or physical limitations that would prevent the subject from interacting with the device as intended
- 2. Any known skin allergy or sensitivity to the study garment materials that will be next to the skin
- 3. Any breached or compromised skin on the upper body that would be exacerbated by wearing the study garment
- 4. Work with or are frequently around equipment that produces high electromagnetic fields, for example magnetic resonance imaging devices, power supply facilities, or welding equipment
- 5. Any planned surgical or medical procedures during the participation period that would require the subject to remove the study device for more than 12 hours
- 6. Any planned air travel during the participation period
- 7. Pregnancy
- 8. Use of mechanical circulatory support, for example Left Ventricular Assist Device (LVAD) or Total Artificial Heart
- 9. Implanted Cardiac Resynchronization Therapy Defibrillator (CRT-D)

- 10. Simultaneous plan/prescription for Holter monitor, mobile cardiac outpatient telemetry (MCOT), Event Recorder, or in-hospital telemetry.
- 11. Use of any electronic medical device that is worn on or near the body requires Sponsor approval, other than continuous positive airway pressure (CPAP), continuous blood glucose monitor, or pulse oximeter oxygen saturation (SpO₂) monitor.
- 12. Under bust chest circumference greater than 52 inches or less than 28 inches
- 13. Current hospital inpatient

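### The eligibility criteria do not keep out persons whose recordings supported development of the rhythm algorithm, and no analysis sets them apart; an exclusion line, or a recorded flag with a repeat analysis, would protect independence at little cost.

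*Protocol*

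**What the plan says.** **Who may enroll.** Protocol 8 (Eligibility Criteria) states: "Candidates are eligible for participation if they meet all Inclusion Criteria and none of the Exclusion Criteria". The population is adults with an active ICD and LVEF of 40% or less, "measured within the past year (12 months) by echocardiography, nuclear imaging (including MRI), or left ventricular angiography". There are 13 exclusions, the last being "Current hospital inpatient". None mentions earlier sponsor studies or contribution to algorithm-development data.

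**Where the algorithm came from.** Protocol 6 (Previous Clinical Studies) describes two studies in the same kind of patient.
- 3321770: single center, 50 subjects, ejection fraction of 40% or less, two days of wear. Of its data the protocol says: "ECG and accelerometer signals were used to support Rhythm Analysis Algorithm (RAA) development".
- 3330766: six centers, 117 subjects with low ejection fraction, five days of wear. It was a "non-randomized study to collect ECG and accelerometer signals to support RAA development and assess comfort and usability".

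Protocol 6 (Study Rationale) says that the RAA is built into the device under test.

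**What is analysed.** The primary endpoint (SAP 4.1) is the rate of false positive alarms per subject-day, tested against 0.29. The Per-Protocol set depends on eligibility and garment size (SAP 8.2). The subgroups (SAP 4.4), the covariates (SAP 5.1) and the bias controls (SAP 8.5) do not refer to prior participation.

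**The concern.** A test of an algorithm is most convincing in persons who played no part in building it. If a person's ECG shape and noise pattern helped to shape the RAA, the RAA may raise fewer false alarms in that person than in a new patient. Such optimism would lower the observed rate. In a single-arm comparison with a fixed external figure, no concurrent control would cancel it. The estimated inappropriate shock rate is the false-alarm rate times a fixed missed-alarm proportion of 23.1% (SAP 4.3), so it would fall by the same fraction.

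The point also becomes harder to settle later. Protocol 9 (Subject Identification Numbers) gives study-specific numbers and bars the sponsor from collecting names, initials, dates of birth or record numbers on the CRF or in the device data. Unless prior participation is prevented or recorded, the study database as described gives the sponsor no means of linking a subject to an earlier study.

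Earlier validation does not fill the gap. Protocol 6 (Study Rationale) reports validation of sensitivity and specificity on previously acquired rhythms, which is not the ambulatory false-alarm rate.

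**Working it through.** **Inputs (SAP 4.2 unless noted).** Null rate 0.29; planned rate 0.145 (50% lower); one-sided level 2.5%; variance-to-mean ratio 14; intra-site correlation 0.026; wear of 14 h/day. Protocol 8 gives 130 subjects, about 10 sites and about 30 days.
- Worn days per subject: 30 × 14/24 = 17.5.
- Design effect with n subjects at 10 sites: DE = 1 + (n/10 − 1) × 0.026. At n = 130, DE = 1 + 12 × 0.026 = 1.312.

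**Reproducing the plan's figure.** The SAP gives about 105 subjects for 90% power but not the form of the test. On the square-root scale, z = 2(√0.29 − √0.145) × √(17.5n/(14 × DE)), to be compared with 1.96 + 1.28 = 3.24.
- n = 105: DE = 1.247, z = 3.236, power 0.899.
- n = 106: DE = 1.250, z = 3.248, power 0.901.
- n = 130: z = 3.511, power 0.94.

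So 105 is reproduced to within one subject. Other forms with the same inputs give 67 (variance at the alternative), 116 (critical value from the null variance) and 172 (log scale), so the match depends on the form chosen.

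**Effect of overlap.** Let f be the share of subjects from the development studies and r the relative reduction of their rate. The documents give neither; both are assumptions. The pooled rate is m = (rate in new patients) × (1 − f·r).

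If the rate in new patients is exactly 0.29, the one-sided error is Φ((0.29 − m)/SE − 1.96), with SE = √(14 × 1.312 × m/(130 × 17.5)).

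| f | r | m | SE | One-sided error |
|---|---|---|---|---|
| 0 | – | 0.2900 | 0.0484 | 2.5% |
| 10% | 10% | 0.2871 | 0.0481 | 2.9% |
| 10% | 25% | 0.2828 | 0.0478 | 3.5% |
| 20% | 25% | 0.2755 | 0.0472 | 4.9% |
| 30% | 25% | 0.2683 | 0.0465 | 6.8% |

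**At the planned rate.** With f = 20% and r = 25%, 0.145 becomes 0.145 × 0.95 = 0.138, and the derived shock rate moves from 0.145 × 0.231 = 0.0335 to 0.0318 per subject-day. With f = 30% and r = 25%, the alarm rate becomes 0.134. The largest observed rate that still passes solves x + 1.96√(14 × 1.312x/2275) = 0.29, which gives about 0.209. A rate near 0.145 is well below this with or without overlap.

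**Power of a repeat analysis without overlapping subjects.**

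| Subjects kept | DE | Square-root form | Null-variance form |
|---|---|---|---|
| 130 | 1.312 | 0.94 | 0.93 |
| 117 (f = 10%) | 1.278 | 0.92 | 0.90 |
| 104 (f = 20%) | 1.244 | 0.90 | 0.87 |

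**The case against.** The strongest reply is that this is a precaution against an overlap that nobody has shown. Much of that stands, and several stronger readings should be set aside.

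- *That the endpoint is measured on the development data.* It is not. The alarms counted come from new recordings of about 30 days on production-equivalent devices (Protocol 7 and 12). The development signals came from second- and third-generation prototypes, and the 3321770 data also led to garment and electrode changes. Only persons could overlap, and noise seen with an older garment may not carry over.
- *That 50 + 117 = 167 former subjects are available.* This is not a realistic pool. Candidates need an active ICD, no CRT-D and an LVEF reading within 12 months; the SAP dates 3330766 to September 2017 and is itself dated March 2019. At 18 per site, six or seven former centers could enroll at most 108 or 126 subjects, and nothing shows that any former center takes part.
- *That former subjects are easier to recruit, or selected for tolerance or good signal.* No passage says so, and SAP 8.5 asks for consecutive eligible subjects. That control does not remove the gap, however, because former subjects can be eligible.
- *That prior participation is not recorded.* The CRF is not among the documents. One can say only that the listed Visit 1 procedures do not mention it and no planned analysis uses it.
- *That the error rate is in fact inflated.* The table rests on assumed f and r at a true rate of exactly 0.29. The protocol says only that signals supported development, and every device runs at default settings.

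What remains is that the documents allow the overlap and would leave it invisible in the analysis.

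**Conclusion.** The gap is real but modest. Persons from the algorithm-development studies may enroll, and no analysis set, subgroup, covariate or sensitivity analysis identifies them. Any optimism in them would lower the reported alarm rate, and the shock rate derived from it, by the fraction f·r: 1% at f = r = 10%, and 5% at f = 20%, r = 25%.

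The rise in one-sided error, to about 2.9% and 4.9% in those two cases, applies only if the rate in new patients is exactly 0.29 and the assumed f and r are right. At the planned 0.145 the conclusion would be unlikely to change. The overlap may be zero.

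The plan is therefore not wrong as written. This is an inexpensive improvement that would let the sponsor state, rather than leave open, that the test sample is independent of development.

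**What to change.** Add one exclusion to Protocol 8 and to the Protocol Summary: prior participation in 3321770, 3330766 or any other study whose recordings were used to develop or tune the RAA. Because the Per-Protocol set requires the eligibility criteria to be met, it would then also leave out anyone enrolled in breach of this.

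If enrollment has begun, record prior participation (yes/no) at Visit 1, and ask subjects already enrolled at the next weekly call or at Visit 2. Pre-specify in SAP 5.1 a repeat of the primary analysis without those subjects, through an amended SAP before the primary analysis, as SAP 9 provides. Report the number of such subjects even if it is zero.

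Cost: one eligibility line, or one CRF field and one extra model fit. With the exclusion a few candidates may be lost, but enrollment stays at 130 and power is unchanged. With the repeat analysis, power falls slightly, as tabulated above.
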